### 11.8.6 Analyses Strategy for Pooling Trial Centers

In order to have an adequate number of subjects represented from each trial site, data from any site that enrolls 3 or less subjects will be evaluated as a pooled site in the primary or secondary endpoints analysis.

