### 11.3 Patient Randomization

#### Part 1

It was planned that approximately 320 eligible patients would be randomized, in order to obtain 306 evaluable patients (i.e., patients who received any test drug and have at least one post-surgical pain intensity score). It had been estimated that 5% of randomized patients may not receive any test drug due to unforeseeable intra-operative exclusion. Patients would be randomized in a 1:1 ratio to receive one of two treatments based on a computer-generated randomization schedule prepared before the study:

- Treatment Group 1: SABER®-Bupivacaine 5 mL (132 mg/mL, 660 mg bupivacaine base)
- Treatment Group 2: Sterile normal saline 5 mL (0.9% sodium chloride injection, USP) (placebo)

Due to the early administrative stopping, only approximately 90 subjects will be enrolled and randomized in Part 1.

#### Part 2

Approximately 274 eligible patients will be randomized, in order to obtain 264 evaluable patients (i.e., patients who are randomized and received any test drug). It has been estimated that 4% of randomized patients may not receive any test drug due to unforeseeable intra-operative exclusion. Patients will be randomized in a 1:1 ratio to receive one of two treatments based on a computer-generated randomization schedule prepared before the study:

- Treatment Group 3: SABER®-Bupivacaine 5 mL (132 mg/mL, 660 mg bupivacaine base)
- Treatment Group 4: Bupivacaine HCl without epinephrine, 15 mL of 0.5% solution (75 mg)

For both Part 1 and 2, the randomization will be balanced by using randomly permuted blocks (block size of 4) and will be stratified by sex. The rationale for stratification by sex was differences in pain response reported in the literature for both acute/chronic pain ([Fillingim et al, 2009](#)), postoperative pain studies in cholecystectomy ([De Cosmo et al, 2008](#); [Uchiyama et al, 2006](#)) and a previous laparoscopic cholecystectomy trial (C803-025, Cohort 2) conducted by DURECT. [De Cosmo et al](#) found that females had a higher mean pain score ( $4.3 \pm 2.1$ ) than males ( $2.9 \pm 1.6$ ) during 24 hours postoperatively ( $p=0.003$  from repeated measure ANOVA). A significant sex effect on 24-hour postoperative pain was also reported by [Uchiyama et al](#).

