If a given study center approaches randomization of 20% of the total number of evaluable subjects (264) into Part 2 of the trial, the Sponsor will assess the appropriateness of allowing the center to continue randomizing additional subjects into the trial based upon factors such as monitored site performance including documentation and protocol compliance. An IWRS system will be used to assign subjects to a treatment group.

If all Screening (i.e. pre-operative) Inclusion/Exclusion criteria are met, randomization can be done up to 1 business day prior to surgery. In the event that a randomized patient does not have the surgical procedure for unforeseen circumstances (such as conversion to open surgery, or the need to use more than 4 laparoscopic ports) or does not receive any test drug, replacement of the patient has been planned. IWRS system will be algorithmically instructed to issue the appropriate randomization replacement and to ensure the balance of treatment as planned. Precise details on the IWRS algorithm will be described in the IWRS specifications.

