##### *Alternate hypothesis:*

There is a difference in analgesic effect between subjects treated with SABER®-Bupivacaine and those treated with bupivacaine HCl, as measured by pain intensity on movement scores over 0-48 hours following test drug administration, with adjustment for sex effect and imputation for missing pain scores.

The pain scores will be analyzed by a mixed effect ANOVA model of repeated measures (MMRM). The model includes the following fixed effects: sex stratum, treatment, sex by

treatment, time, interaction of treatment and time, study site and interaction of study site and treatment, with time as the repeating factor and subject as a random effect.

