#### 11.8.2 Secondary Efficacy Endpoints

For all secondary efficacy endpoints, data from SABER®-Bupivacaine arm in Part 1 will be combined with the same treatment arm in Part 2. The integrated data will be compared to Bupivacaine HCl.

The key secondary efficacy endpoint:

- Pain intensity on movement measured at scheduled time points from 0-72 hours following test drug administration, adjusted for prior rescue medication use and analyzed by a mixed effect ANOVA model of repeated measures (MMRM).

The adjustment algorithm for rescue medication use is the same as described for the primary endpoint in [Section 11.8.1](#).

Additional secondary efficacy endpoints:

- Total IV morphine-equivalent dose of rescue opioids used during 0-72 hours following test drug administration (standard conversion factors will be used to convert different opioids to IV morphine-equivalents; CCI)

- Composite endpoint of Silverman's Integrated Analgesic (SIA) assessment score (Dai et al, 2013 and Silverman et al, 1993) over 0-72 hours following test drug administration
- Proportion of patients taking no opioid rescue medication from PACU discharge until 72 hours after test drug administration
- Time to first opioid rescue medication use after discharge from the PACU
- Time to PACU discharge eligibility as assessed by mPADSS (Chung, 1995; Awad and Chung, 2006).

The total IV morphine-equivalent dose of opioid rescue medication used during the first 72 hours post-dose will be analyzed by an ANOVA model adjusted for the stratification or by the van Elteren test (a stratified Wilcoxon Rank Sum test), depending on whether normality assumptions have been met.

A composite endpoint, Score of Integrated Analgesia (SIA) (Dai et al, 2013 and Silverman et al, 1993), that integrates pain assessment score with opioid use will be derived at 24, 48 and 72 hours post-surgery. The score derived for each subject represents a sum of the ranks (ranging from -200 to 200 with -200 being the best case and 200 the worst case). SIA will be analyzed by repeated measures ANOVA. The model will have treatment, sex, sex\*treatment interaction and study site as the main effects, subject as the random effect and time as the repeating factor.

[figure not shown]
The categorical efficacy endpoint, proportion of patients taking no opioid rescue medication will be compared between the two treatment groups using the Cochran-Mantel-Haenszel (CMH) test stratified by sex.

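### Sites are pooled by total count, not by arm, and randomisation is not stratified by site, so an empty site-by-treatment cell can make the all-site primary treatment effect non-estimable, with no fallback specified.

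*Combined protocol and SAP*

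**What the plan says.** Four parts of the combined protocol and SAP bear on this.

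- **Pooling (Section 11.8.6).** "data from any site that enrolls 3 or less subjects will be evaluated as a pooled site in the primary or secondary endpoints analysis". The trigger is the site total. There is no minimum per arm, and the section does not say whether the count covers Part 2 only, both parts, or the mITT set.
- **Randomisation (Section 11.3).** Allocation in Part 2 is 1:1, and "the randomization will be balanced by using randomly permuted blocks (block size of 4) and will be stratified by sex". Assignment is through an IWRS. The synopsis and Section 5.4 also name sex as the only stratum.
- **Primary model (Section 11.8.1, after the alternate hypothesis).** Besides the sex, treatment and time terms, the fixed effects include "study site and interaction of study site and treatment, with time as the repeating factor and subject as a random effect". No weighting of sites is given for the overall treatment effect, and no rule for an empty site-by-treatment cell.
- **Secondary endpoints (Section 11.8.2).** The Part 1 SABER-Bupivacaine arm is added to the Part 2 arm, and "The integrated data will be compared to Bupivacaine HCl".

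The primary analysis itself uses Part 2 mITT patients only (Sections 11.4, 11.5 and 11.8).

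**The concern.** With a fixed site-by-treatment term, each site has its own treatment effect, and the overall effect is a weighted average of these. A site with patients in one arm only supplies no information on its own treatment effect. Any overall effect that gives that site weight then has no estimate.

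Nothing visible in the plan prevents this. Blocks run within sex across the trial, so arms need not balance within a site, and the pooling rule looks only at totals. The primary test is the gate for every secondary test (Section 11.8.4). If the planned contrast failed, someone would have to choose between leaving the site out, pooling it or dropping the interaction. Arm counts within sites become visible only once treatment codes are known, so that choice could fall after unblinding unless it is fixed beforehand.

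**Working it through.** **Inputs.** Part 2: about 274 randomised for 264 evaluable, 4% not dosed, 1:1 (Section 11.3). Sites: 5 to 25 (Section 6.1). Sponsor review when a site nears 20% of 264, that is 0.20 × 264 = 52.8 patients; no minimum site size (Sections 6.1, 7.1, 11.3). The plan states no figure for site-by-arm counts. Its enrolment figure reproduces: 264 / 0.96 = 275, against about 274.

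**Step 1: estimability.** Write D_s for the treatment effect at site s and the overall effect as the sum of w_s × D_s. If site k has one arm only, D_k appears in no fitted cell mean, so the sum is estimable only when w_k = 0. This was checked on a fixed-effect design with the Section 11.8.1 terms and six sites of 12, 10, 9, 8, 6 and 4 patients (total 49). A residual of 0 means estimable.

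| Design | Site weights | Residual |
|---|---|---|
| All cells filled | equal or by patient number | 0 |
| 4-patient site all in one arm | equal | 0.167 (= 1/6) |
| 4-patient site all in one arm | by patient number | 0.082 (= 4/49) |
| 4-patient site all in one arm | five complete sites only | 0 |
| Same data, site-by-treatment dropped | equal or by patient number | 0 |
| Same data, that site merged with another | equal | 0 |

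The residual equals the weight placed on the one-armed site.

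**Step 2: chance for one site.** With 1:1 allocation not balanced within site, P(one arm empty | n) ≈ 2 × 0.5^n.

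- n = 4: 2 × 0.0625 = 12.5%
- n = 5: 6.3%
- n = 6: 3.1%
- n = 8: 0.8%

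Simulating central blocks of 4 within sex gave 12.4%, 5.9%, 3.0% and 0.7%, so the blocks give little protection. The same formula applies to the pooled site when it is small: with 1, 2 or 3 patients in all it is one-armed with probability 100%, 50% or 25%.

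**Step 3: chance for the trial.** Trials were simulated with central sex-stratified blocks of 4 and the 3-or-less rule applied. Site sizes were either equal in expectation or drawn from gamma distributions (shape 2, 1 or 0.5). Site sizes and sex mix are assumptions, because the plan gives neither.

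| Sites | Equal expected size | Unequal, unpooled sites only |
|---|---|---|
| 10 | near 0 | 3–9% |
| 15 | near 0 | 10–16% |
| 20 | about 5% | 17–25% |
| 25 | 18–22% | 24–37% |

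Counting an empty arm in the pooled site as well, the unequal-size range is roughly 14–36% across 10 to 25 sites. At 10 sites most of that comes from the pooled site. With 5 unequal sites the unpooled-only figure is about 1–3%. The runs differ in detail: some start from 274 randomised with 4% not dosed and no ceiling on site share, others from 264 with no site above about 20%. The ranges therefore overlap and do not nest exactly.

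**Step 4: which patients are counted.** If enrolment in Section 11.8.6 means Part 1 (about 90) plus Part 2, a site can escape pooling on its Part 1 patients and still have very few in the primary analysis. The unequal-size figure for unpooled sites then becomes about 11–19% at 10 sites and 56–64% at 25.

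**The case against.** The strongest reply is that an estimate and p-value could still be produced. That is right. A contrast over the complete sites stays estimable, and software can return a Type III test. A reader might infer that the primary effect cannot be estimated at all, or that no choice of weights helps. The documents do not support either: Section 11.8.1 never defines the effect as an average over all sites, and zero weight on the one-armed site restores estimability. What stands is that such a contrast answers a different question, and the plan does not pre-specify it.

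A reader might also infer that the key secondary analysis is certain to fail at any site active only in Part 1. Section 11.8.2 does not list that model's fixed effects, and the one repeated-measures model it spells out, for the SIA score, has site as a main effect without site-by-treatment. The problem arises only if the primary model is carried over and some site has 4 or more Part 1 SABER-Bupivacaine patients but no Part 2 enrolment. Whether such a site exists is unknown.

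Third, a repair after unblinding is not inevitable. Section 11.11 has deviations documented before unblinding, Section 11.6 refers to a separate SAP, parts of Section 7.1 are redacted, and IWRS details are left to its specifications. A site constraint or fallback could sit there. Site totals are also visible while blinded, so the pooling threshold could be raised. These points lower the risk. They do not supply the missing rule in Sections 11.3, 11.8.1 and 11.8.6, which are readable on this point and contain none.

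**Conclusion.** The concern holds as a gap in the confirmatory analysis. The pooling rule, the sex-only stratification and the fixed site-by-treatment term together allow an empty cell. In that event the all-site treatment effect is not estimable and the plan names no substitute.

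It is a risk, not a certainty. It is low with few large sites or with 10 to 15 equal ones. It is about 5% for 20 equal sites and 18–22% for 25. With unequal recruitment over 10 to 25 sites it is roughly 14–36% counting the pooled site. Counting unpooled sites only, it is about 3–9% at 10 sites and 24–37% at 25. These figures rest on assumed site sizes, about 264 analysed patients, and central blocks that are not balanced within site. For the key secondary endpoint the point is conditional on its using the same model.

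**What to change.** Before unblinding, amend Sections 11.8.1 and 11.8.6 in one of two ways.

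1. **Simplest.** State that the primary treatment effect is estimated from the model with site as a main effect only, and move site-by-treatment to a supportive analysis. This restores estimability in the Step 1 example without changing the pooling rule and needs no treatment codes.
2. **Alternative.** Keep site-by-treatment, but pool any site without at least 1 analysed patient in each compared arm. Use an algorithm programmed before unblinding and applied separately to each analysis set, and drop site-by-treatment from that model if an empty cell remains. One patient per arm is enough for estimability; a higher minimum is a matter of preference.

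Either way, say which patients are counted for pooling (for the primary analysis, the Part 2 mITT patients), and list the fixed effects of the key secondary model in Section 11.8.2.

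The cost is about a paragraph of wording. Under the first option, differences between sites are examined only as a supportive analysis. Under the second, a few more small sites are pooled, and the site groups may differ between analysis sets.

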### 11.9 Interim Analyses and Data Monitoring

There is no planned interim analysis. An interim analysis will only be implemented if the Safety Assessment Committee (SAC) stops the trial (see 11.9.1) for safety. Safety data will be monitored in a blinded manner throughout the study in accordance with the Safety Monitoring Plan. Unblinded review of SAEs will be conducted by the SAC at its discretion, in accordance with the SAC Charter and as described below in Section 11.9.1. The Safety Assessment Committee comprises three members that are independent of the study (medical professionals and a statistician).

#### 11.9.1 Study-Stopping Criteria

The following study stopping criteria, extracted from the SAC Charter CCI will be used for Part 2 of the trial.

##### 11.9.1.1 General Provisions

- The Sponsor medical monitor will carefully and routinely monitor the blinded safety data for any occurrence of SAEs, will promptly provide all SAE data to the SAC and will convene an SAC meeting if any safety events require an immediate review by the committee.
- The period of observation will be based on safety data reported during the 60-day post-treatment period.
- The SAC will be responsible for determining whether SAEs provided to them meet the requirements for stopping the trial, as set forth in SAC Charter sections 4.2 and 4.3. To make this determination, the SAC at its discretion, may choose to un-blind the case for detailed examination.
- The bupivacaine control patients are receiving standard of care for this low-risk surgical procedure and will be at no greater risk than those undergoing laparoscopic cholecystectomy outside of the PERSIST clinical trial. For that reason, SAEs occurring in the control group will not constitute trial-stopping events, although they could prompt revision of the trial protocol if deemed appropriate.

##### 11.9.1.2 Stopping due to Fatal Events

The SAC will convene in the event that any post-treatment fatality has been reported. The reported fatality will be un-blinded and all available clinical data will be investigated and

evaluated by the SAC. The SAC will recommend stopping the trial if, in its judgment, all of the following provisions (1), (2) and (3) have been met:

- (1) SABER-Bupivacaine was administered to the patient.
- (2) The fatal event had a temporal relationship to administration of SABER-Bupivacaine
- (3) A clear alternate cause for the fatal SAE is not readily apparent

If the SAC recommends that the trial not be stopped because the fatality under review fails to meet the stopping criteria, it may instead recommend revisions to the study protocol to enhance patient safety and may also recommend a pause in enrollment until such revisions can be implemented.

#### **11.9.1.3 Stopping due to Non-Fatal Serious Adverse Events**

The SAC will review all SAEs reported during the PERSIST trial. The SAC may un-blind the patient data relating to any SAE it wishes to examine in detail for the purpose of determining whether stopping criteria have been met. The study will be stopped upon the occurrence of three non-fatal SAEs (including any wound hematoma, dehiscence, pruritus, and bruising), each of which, in the judgment of the SAC, meets all of the following provisions (1), (2), and (3):

- (1) SABER-Bupivacaine was administered to the patient.
- (2) The SAE had a temporal relationship to administration of SABER-Bupivacaine
- (3) A clear alternate cause for the SAE is not readily apparent

If the SAC recommends that the trial not be stopped because the SAEs under review fail to meet the stopping criteria, it may instead recommend revisions to the study protocol to enhance patient safety and may also recommend a pause in enrollment until such revisions can be implemented.

### **11.10 Statistical Analysis of Safety Endpoints**

#### **11.10.1 Safety Variables and Summaries**

Safety summaries will be based on the safety population. The safety population will include all subjects treated with SABER®-Bupivacaine 5 mL (660 mg bupivacaine base) or 0.9% sterile normal saline 5 mL (placebo) in Part 1; and all subjects treated with SABER®-Bupivacaine 5 mL or 15 mL of 0.5% bupivacaine HCl in Part 2. It will include summaries in the form of tables and patient listings by three treatment arms; SABER®-Bupivacaine 5 mL (660 mg bupivacaine base), 15 mL of 0.5% solution bupivacaine HCl (75 mg) or 0.9% sterile, normal saline 5 mL (placebo).

Safety variables include:

- Subject incidence rate of adverse events (both pre-specified patient-reported AEs solicited on LogPad through Study Day 4 [POD 3], as well as spontaneous AEs reported either by patient or investigator)

- Subject incidence rate of solicited AEs occurring in the first 6 hours after dosing of test drug.
- Time to the first occurrence of the solicited AEs
- Time to PACU discharge
- Change in standard 12-lead ECG at Screening, Visit 6 (Study Day 29), and Visit 7 (Study Day 60)
- Change in safety Laboratory Tests (serum chemistry, hematology, urinalysis) (Screening, Study Day 4, Study Day 29, Study Day 60)
- Change in vital Signs (heart rate, blood pressure, temperature, respiratory rate) (at each scheduled visit) and height, weight, BMI (Screening, Study Day 29, Study Day 60)
- CCI 

The subject incidence rate (number and percentage) of treatment emergent adverse events will be tabulated in each treatment group by MedDRA System Organ Class and Preferred Term. Summaries will also be presented by the severity of the adverse event and by relationship to test drug.

The individual rate of solicited patient-reported AEs (dizziness, somnolence, constipation, nausea, vomiting, pruritus, headache, dysgeusia, hypoesthesia, and paresthesia) will be derived. The risk ratio and 95% confidence interval (CI) for the individual AE rate will be presented with saline placebo and bupivacaine HCl as the control groups. For example, if the 95% CI for the risk ratio contains 1, the AE risk is considered comparable between the active and control groups.

Time to the first occurrence of the solicited AEs will be analyzed by the Kaplan Meier method. For subjects who do not have the AE, the observation will be censored in the analyses. Median time and 95% confidence interval (CI) will be determined.

The change in safety laboratory, ECG and vital signs parameters from baseline will be analyzed by shift tables. Descriptive statistics (means, medians, SD, minimum/maximum) for the safety variables and change from baseline will be summarized. Subjects found to have abnormal safety values considered clinically significant will be summarized.

The presence/absence of surgical site AEs (see definitions in [Section 9.2.6](#)) will be tabulated by treatment and study visit. The overall rate of each AE across study visits will be tabulated by treatment. The risk ratio and 95% CI will be derived for each AE. Known risk factors related to wound healing, such as being diabetic or having higher BMI, may be used for adjusted relative risk if they are not balanced by randomization alone. Time to the first occurrence of each AE

will be derived from the end of surgery. The data will be censored for subjects who do not have the AE. The median, 95% CI, 25th and 75th percentile for the time to each AE will be summarized by treatment. The time to resolution of each AE will also be derived and summarized.

CCI

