#### 5.4.1 Dose

Test drug for the trial consists of a single administration of one of two treatments based on a computer-generated randomization schedule prepared before the study:

##### Part 1

- Treatment Group 1: SABER®-Bupivacaine 5 mL (POSIMIR®)(132 mg/mL, 660 mg bupivacaine base)
- Treatment Group 2: Sterile normal saline 5 mL (0.9% sodium chloride injection, USP) (placebo)

##### Part 2

- Treatment Group 3: SABER®-Bupivacaine 5 mL (POSIMIR®)(132 mg/mL, 660 mg bupivacaine base)

- Treatment Group 4: Bupivacaine HCl without epinephrine, 15 mL of 0.5% solution (75 mg)

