#### 11.4 Definition of Analysis Population

**ITT Population:** The ITT population will consist of all randomized patients in both Part 1 and Part 2 independent of their exposure to test drug or completion of surgery. However, the primary efficacy analysis will include only Part 2 data.

**Safety Population:** The Safety population will consist of all subjects in both Part 1 and Part 2 who received any amount of test drug. The Safety population will be used for all safety analyses.

**Modified Intention-to-Treat (mITT) Population:** All randomized patients in both Part 1 and Part 2 who receive any test drug. However, the primary efficacy analysis will include only Part 2 data.

All efficacy endpoints will be analyzed using the mITT set.

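### Section 11.10.1 reads an AE risk-ratio CI that contains 1 as comparable risk, which a trial with about 45 saline patients cannot support; it also leaves unstated which SABER patients enter each ratio

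*Combined protocol and SAP*

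**What the plan says.** Section 11.4 defines the safety set across both Parts: "The Safety population will consist of all subjects in both Part 1 and Part 2 who received any amount of test drug". It applies that set to every safety analysis. Section 5.4.1 defines four treatment groups: SABER and saline in Part 1, SABER and bupivacaine HCl in Part 2. Section 11.10.1 then presents safety in three columns: "It will include summaries in the form of tables and patient listings by three treatment arms".

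For the ten solicited AEs, the risk ratio and 95% CI "will be presented with saline placebo and bupivacaine HCl as the control groups". The section adds, as an example of interpretation, that "if the 95% CI for the risk ratio contains 1, the AE risk is considered comparable between the active and control groups". For surgical-site AEs, "The risk ratio and 95% CI will be derived for each AE"; the comparability sentence is not repeated there. Wound-healing risk factors "may be used for adjusted relative risk if they are not balanced by randomization alone". Treatment-emergent AEs "will be tabulated in each treatment group by MedDRA System Organ Class and Preferred Term".

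No visible sentence says which SABER patients form the numerator of each ratio, and none stratifies by Part. Sections 11.5 and 11.8.2 do state outright that the two SABER arms are combined, but for secondary and exploratory efficacy.

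**The concern.** There are two separate problems.

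- **The comparability rule.** Whether a CI contains 1 depends on the number of events as much as on the true risk. With a small control arm, the rule returns comparable risk for most AEs even if the drug doubles them. The saline ratio is the trial's only placebo-controlled safety comparison, and it has the smallest control group. A conclusion of comparable tolerability could therefore follow from low precision alone.
- **The SABER group in each ratio.** Saline exists only in Part 1 and HCl only in Part 2. If one combined SABER arm is compared with each, some SABER patients were never randomised against that control. Part 1 is enrolled before Part 2 (Synopsis), and its end depends on sites becoming ready for Part 2 (Section 11.2), so calendar time and site mix can differ. The only adjustment mentioned is optional, covers wound-healing factors, and presumes balance from randomisation, which a combined SABER arm does not have.

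**Working it through.** **Inputs from the documents.** Part 1 has about 90 patients at 1:1, so 45 per arm. Part 2 has 132 treated per arm, 264 in all. The plan's inflation reproduces: 264/0.96 = 275 against the stated 274 (274 × 0.96 = 263.0).

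**Assumptions.** All 90 Part 1 patients are dosed. Control AE rates of 10% and 20% are illustrative, because the documents give none. The CI is a Wald interval on the log risk ratio, with 0.5 added when a count is zero.

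**1. The comparability rule, with equal rates in the two Parts and a true risk ratio of 2.** SE = √[(1−p₁)/(p₁n₁) + (1−p₀)/(p₀n₀)]. With p₀ = 10% and p₁ = 20%, the CI at the expected counts is:

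| Comparison | SE | CI around 2.0 |
|---|---|---|
| Saline, within Part (45 v 45) | √(0.0889 + 0.2000) = 0.537 | 0.70 to 5.73 |
| Saline, combined SABER (177 v 45) | √(0.0226 + 0.2000) = 0.472 | 0.79 to 5.04 |
| HCl, within Part (132 v 132) | √(0.0303 + 0.0682) = 0.314 | 1.08 to 3.70 |
| HCl, combined SABER (177 v 132) | √(0.0226 + 0.0682) = 0.301 | 1.11 to 3.61 |

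Versus saline, the interval contains 1 even when the data show the full doubling. Summing binomial probabilities over all outcomes gives the chance that the CI contains 1, so that the rule says comparable:

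| Control rate | Saline, combined | Saline, within Part | HCl, combined | HCl, within Part |
|---|---|---|---|---|
| 10% | 77% | 80% | 34% | 39% |
| 20% | 34% | 48% | 3% | 5% |

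**2. Shares under the combined reading.** The denominator is the SABER patients. Not randomised against saline: 132/177 = 74.6%. Not randomised against HCl: 45/177 = 25.4%. With 4% of Part 1 undosed, the shares are 75.3% and 24.7%. If Part 1 ends at 80 to 100 patients, the saline share runs from 76.7% to 72.5%.

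**3. Conditional bias with no drug effect.** Let r be the Part 1/Part 2 ratio of background rates (assumed). Expected RR v HCl = (45r + 132)/177; expected RR v saline = that value divided by r.

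| r | v saline | v HCl |
|---|---|---|
| 0.80 | 1.19 | 0.95 |
| 1.0 | 1.00 | 1.00 |
| 1.1 | 0.93 | 1.02 |
| 1.25 | 0.85 | 1.06 |
| 1.5 | 0.75 | 1.13 |

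Versus saline, at r = 1.0, 1.1, 1.25 and 1.5, the combined CI lies falsely below 1 in 3%, 6%, 13% and 33% of trials at a 30% Part 2 rate (about 2% within Part). At a 10% rate the figures are 3%, 4%, 7% and 12% (about 1–1.5% within Part). In the other direction, at r = 0.80, it lies falsely above 1 in 5% at a 30% rate and in about 0.0% at a 10% rate.

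**4. Precision cost of staying within Part.** Log-CI width ratio v saline: √[(2/45)/(1/177 + 1/45)] = 1.26. Versus HCl: √[(2/132)/(1/177 + 1/132)] = 1.07. For a 1% event, 45 × 0.01 = 0.45 cases are expected per Part 1 arm. The chance that at least one Part 1 arm has none is 1 − (1 − 0.99⁴⁵)² = 87%.

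**The case against.** The strongest reply is to the second point. Combining in the ratios is an inference. A three-column layout governs display and need not fix the numerator of each ratio. Where the plan wants SABER arms combined, for efficacy, it says so, and it tabulates treatment-emergent AEs by treatment group, a term Section 5.4.1 uses for four numbered groups. Parts of Section 11.10.1 are redacted, and Sections 11.6 and 11.11 refer to a separate SAP, so a rule may exist. This stands, although the two-Part safety set in Section 11.4 makes combining the natural reading.

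A reader might infer that the saline ratio is confounded. The documents do not support that. Dose, eligibility, anaesthesia, surgical and rescue rules are shared by the Parts, no AE rates by Part are given, and every r other than 1 above is assumed. A reader might also point to the waived Day 60 visit for patients enrolled before Amendment 5 was approved at their site (Section 7.4.10). No size can be put on that, and it cannot affect AEs solicited through postoperative day 3.

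Moving wholly within Part is also a trade-off. For a true doubling at a 20% Part 2 rate, detection versus saline, within Part v combined, is 46% v 72% at r = 0.91, 52% v 66% at r = 1.0, 57.5% v 60% at r = 1.1 and 67% v 51% at r = 1.25. An analyst could reasonably want the full SABER exposure shown. This stands, and it is why the combined estimate should be kept.

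These ratios lie outside the testing sequence in Section 11.8.4, and the stopping criteria in Section 11.9.1 rest on case review. That limits the consequences. None of these replies rescues the comparability rule, which fails whichever SABER patients are used.

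**Conclusion.** The comparability rule is wrong as written and should be changed. With equal Parts and a true doubling, it would declare comparability with saline in about 77–80% of trials at an assumed 10% control rate and 34–48% at 20%. Versus HCl the figures are 34–39% and 3–5%. They rest on 45 and 132 patients per arm and on the assumed rates.

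The unstated SABER group is a minor point of clarification. The shares of about 75% and 25% follow from the planned sizes if the arms are combined. Bias is zero if the Parts have equal AE rates and small versus HCl, which is the comparison in the trial objective (expected ratio 1.02 to 1.06 at r of 1.1 to 1.25). It could matter versus saline only if rates differ. The stronger statement, that the plan commits to a biased saline comparison, goes beyond the visible text.

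**What to change.** 1. In Section 11.10.1, delete the sentence that equates a CI containing 1 with comparable risk. Report the estimate and CI, and state that such an interval is not evidence of comparable risk. This costs nothing.
2. In the same section, name the SABER patients in each solicited-AE and surgical-site ratio. Present SABER v saline within Part 1 and SABER v HCl within Part 2 as the randomised comparisons. Keep the combined-SABER estimate as a supplement labelled partly non-randomised, and give counts where a Part 1 ratio cannot be estimated.

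The cost of the second change is wording and extra table columns, with no new data. The within-Part CI is about 26% wider on the log scale versus saline and 7% wider versus HCl. For 1% events, counts would usually replace the Part 1 ratio. The plan keeps Part 1 data blinded until Part 2 is complete, so both changes can be specified before unblinding. If the separate SAP already names the SABER group, a cross-reference is enough for that part of the second change.
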